10.0 Pharmaceutical Information

A list of the adverse events and potential risks associated with the investigational or commercial agents administered in this study can be found in Section 9.1.

10.1 Pharmaceutical Accountability

Drug accountability logs will be maintained for all agents used under this protocol. These logs shall record quantities of study drug received and quantities dispensed to patients, including lot number, date dispensed, patient identifier number, patient initials, protocol number, dose, quantity returned, balance remaining, and the initials of the person dispensing the medication.

10.2 Carboplatin

Product description: PARAPLATIN® (carboplatin) for Injection, USP is supplied as a sterile, lyophilized white powder available in single-dose vials containing 50 mg, 150 mg, and 450 mg of

A Phase II Trial Evaluating Quality of Life After HIPEC in Patients with Stage IIIC and IV Ovarian, Fallopian Tube or Primary Peritoneal Carcinoma
Wake Forest Baptist Comprehensive Cancer Center (WFBCCC)
CCCWFU 83216

carboplatin for administration by intravenous infusion. Each vial contains equal parts by weight of carboplatin and mannitol.

Solution preparation: Immediately before use, the content of each vial must be reconstituted with either Sterile Water for Injection, USP, 5% Dextrose in Water (D5W), or 0.9% Sodium Chloride Injection, USP, according to the following schedule:

Vial Strength	Diluent Volume
50 mg	5 mL
150 mg	15 mL
450 mg	45 mL

These dilutions all produce a carboplatin concentration of 10 mg/mL. PARAPLATIN can be further diluted to concentrations as low as 0.5 mg/mL with 5% Dextrose in Water (D5W) or 0.9% Sodium Chloride Injection, USP.

Storage requirements: Unopened vials of PARAPLATIN are stable for the life indicated on the package when stored at 25°C (77°F); excursions permitted from 15°-30°C (59°-86°F) [see USP Controlled Room Temperature]. Protect from light.

Stability: When prepared as directed, PARAPLATIN solutions are stable for 8 hours at room temperature (25°C). Since no antibacterial preservative is contained in the formulation, it is recommended that PARAPLATIN solutions be discarded 8 hours after dilution.

Route of administration: PARAPLATIN is usually administered by an infusion lasting 15 minutes or longer. No pre- or post-treatment hydration or forced diuresis is required. Parenteral drug products should be inspected visually for particulate matter and discoloration prior to administration.

Disposal: Caution should be exercised in handling and preparing PARAPLATIN (carboplatin) for Injection, USP. Several guidelines on this subject have been published. To minimize the risk of dermal exposure, always wear impervious gloves when handling vials containing PARAPLATIN (carboplatin) for Injection, USP. If PARAPLATIN (carboplatin) for Injection, USP or solutions containing PARAPLATIN (carboplatin) for Injection, USP contact the skin, immediately wash the skin thoroughly with soap and water. If PARAPLATIN (carboplatin) for Injection, USP or solutions containing PARAPLATIN (carboplatin) for Injection, USP contact mucous membranes, the membranes should be flushed immediately and thoroughly with water.

11.0 Correlative Studies

None

12.0 Data Management

The Appendices contain master copies of the case report forms (CRFs) to be used for this protocol.

Note: If the patient does not have protocol therapy at surgery, it is still necessary to submit Day 0 data and the No HIPEC Follow-Up form annually.

Informed consent document

EPIC

A Phase II Trial Evaluating Quality of Life After HIPEC in Patients with Stage IIIC and IV Ovarian, Fallopian Tube or Primary Peritoneal Carcinoma
Wake Forest Baptist Comprehensive Cancer Center (WFBCCC)
CCCWFU 83216

Protocol registration Form (Appendix B)	WISER
FACT-O, FACT-GOG-NTX4, FACT/GOG-AD (Appendices H, I, J)	WISER
Follow-up form (Appendix F)	WISER
RECIST measurement form (Appendix G)	WISER
Adverse Events Log (Appendix K)	WISER

The Protocol Registration Form and signed Informed Consent Form should be completed and faxed to the WFBCCC Registrar in order to enroll and randomize participants. All other CRFs & supporting documents should be faxed to the attention of the Study Coordinator according to the following schedule:

Form	Submission Schedule
Surgery Form	Form and reports within 30 days of surgery
Perfusion Record - HIPEC Form	Form within 30 days of surgery
Adverse Event Log	Form within 7 days of completion of time period.
Follow-Up / Measurement Form	Form and supporting documents within 7 days of mo. 3, 6, and 12
FACT-O, FACT/GOG-AD, FACT/GOG-NTX	Prestudy, , Week 6, months 3 and 6 post-treatment (follow-up)

13.0 Statistical Considerations

13.1 Analysis of Primary Objective

This is a descriptive study. The primary objective is to compare the QOL in patients with advanced ovarian cancer treated with SOC NAC followed by CRS with HIPEC vs. QOL in patients treated with IV chemotherapy at 6 weeks post-treatment presented in Armstrong et al. (2006). Only the patients treated with SOC NAC followed by CRS with HIPEC will be recruited in this study. The summary data of QOL for patients treated with IV chemotherapy collected in Armstrong et al. (2006) will be directly used. The same as Armstrong et al., QOL will be measured using the Fact-O questionnaire and treatment as a continuous outcome. The distribution of QOL at 6 weeks post-treatment will be examined. The descriptive statistics such as mean, standard deviation, median and interquartile range will be calculated. One sample t-test will be used to compare the mean QOL in the study sample to the mean QOL based on Armstrong et al.

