2.0 Objectives

2.1 Primary Objective(s)

- 2.1.1 To compare the QOL in patients with advanced ovarian cancer treated with SOC NAC followed by CRS with HIPEC at 6 weeks post-treatment vs. QOL in patients treated with intravenous-therapy (IV) chemotherapy presented in Armstrong et al. (2006).

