13.3 Power and Sample Size

The power calculation is performed to test the primary objective. It is calculated to compare the mean QOL between the study patients and the mean QOL from Armstrong et al. (2006). Based on Armstrong et al., the standard deviation of QOL at 6 weeks post treatment is 19.2. Fifty patients will be recruited. The dropout rate is anticipated to be very small, around 1 to 2% at 6 weeks post treatment. Assuming 80% power, a two-sided test and a significance level of 20%, the minimal detectable difference of QOL between the study sample and Armstrong et al. is 5.9. If assuming a higher dropout rate, say 10% at 6 weeks post treatment, the minimal detectable difference for QOL is 6.1. Based on Armstrong et al., the mean difference of QOL between the two standard treatments (IV vs. intraperitoneal) is 5.2. We assume that the mean difference between HIPEC and IV can be larger. However, we are also aware that we may not have enough power to detect the difference. This study is for the descriptive purpose. The data collected in this study can be very useful for future research.

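### The primary one-sample t-test treats the published IV-arm mean as known exactly, so its true error rate is above the stated 20% and the detectable difference of 5.9 is too small

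*Combined protocol and SAP*

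**What the plan says.** Section 2.1 sets the primary objective as a comparison between groups of patients: "To compare the QOL in patients with advanced ovarian cancer treated with SOC NAC followed by CRS with HIPEC at 6 weeks post-treatment", against patients given IV chemotherapy in the cited 2006 trial. Section 13.1 repeats this and makes clear that there is no concurrent control: "Only the patients treated with SOC NAC followed by CRS with HIPEC will be recruited in this study". For the comparator, "The summary data of QOL for patients treated with IV chemotherapy collected in" the cited trial are to be used directly. The test is then specified: "One sample t-test will be used to compare the mean QOL in the study sample to the mean QOL based on" that trial.

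Section 13.3 sizes this comparison. From the cited report, "the standard deviation of QOL at 6 weeks post treatment is 19.2". The sample is fixed in advance ("Fifty patients will be recruited"), with 1 to 2% dropout expected at 6 weeks. The operating characteristics follow: "Assuming 80% power, a two-sided test and a significance level of 20%, the minimal detectable difference of QOL between the study sample and" the cited trial is given as 5.9, or 6.1 if dropout is 10%. The section also notes a 5.2-point difference between the IV and intraperitoneal arms of that trial.

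Neither section gives the number of IV-arm patients behind the published mean or the standard error of that mean. Neither makes any allowance for its sampling error.

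**The concern.** A one-sample t-test asks whether the new patients' mean differs from a fixed number. Its standard error is SD/√n for the new patients alone. The objective asks something else: whether HIPEC patients and IV-treated patients differ. The IV mean came from a finite sample, so the variance of the difference has a second term that the planned test sets to zero.

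Three consequences follow. The test rejects more often than 20% when the two populations have the same mean. Its p-value, and any interval built from the same standard error, overstates precision. A test that did hold the 20% level would not have 80% power at 5.9. This is the only inferential test of the primary outcome, and a 20% level is already lenient, so further unacknowledged inflation matters to how a positive result is read.

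**Working it through.** **Inputs.** SD 19.2, two-sided level 20%, power 80%, 50 recruited, dropout 1 to 2% (about n = 49 analysed) or 10% (n = 45), all from section 13.3. Section 3.3 still gives a total of 40; sections 13.3 and 13.4 support 50 (40 plus 10 by amendment), so 50 is used. The number of IV-arm patients with a 6-week score, m, is **not in the documents**. It is assumed over a range, with SD 19.2 in both groups.

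**Step 1: reproduce the plan's figures.** By normal approximation, the one-sample detectable difference is (z₀.₉₀ + z₀.₈₀) × SD/√n.
- n = 49: (1.2816 + 0.8416) × 19.2/7 = 5.82
- n = 45: 2.1232 × 19.2/6.708 = 6.08

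The exact noncentral-t calculation gives 5.87 at n = 49 (5.81 at n = 50) and 6.13 at n = 45, matching the stated 5.9 and 6.1. Other readings do not match at n = 49: one-sided 20% gives about 4.6, two-sided 5% gives about 7.8, and a two-sample formula with equal groups gives 8.2. The stated figures therefore assume a reference mean without error.

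**Step 2: true error rate of the planned test.** If the two populations have equal means, the difference has variance SD²(1/n + 1/m), but the test divides by SD/√n. The statistic is inflated by √(1 + n/m), so the error rate is 2 × P(t with n − 1 df > t₀.₉₀ / √(1 + n/m)).

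For n = 49 and m = 100, the inflation is √1.49 = 1.221. The normal approximation gives 1.2816/1.221 = 1.050 and a two-sided error rate of 29.4%; the t calculation gives 29.2%.

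**Step 3: detectable difference and power with the comparator's variance included.** The standard error becomes 19.2 × √(1/n + 1/m). For n = 49 and m = 100 it is 19.2 × √0.03041 = 3.348, so the detectable difference is 2.1232 × 3.348 = 7.11 (7.12 by two-sample noncentral t). The power columns below are for a two-sample test that holds the 20% level.

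| m (assumed), n = 49 | True error rate of planned test | Detectable difference | Power at 5.9 | Power at 5.2 |
|---|---|---|---|---|
| Fixed reference (as planned) | 20% | 5.9 | 80.3% | 72.6% |
| 1000 | 21.1% | 6.0 | 79.4% | 71.6% |
| 400 | 22.6% | 6.2 | 77.3% | 69.5% |
| 200 | 25.0% | 6.5 | 74.1% | 66.2% |
| 100 | 29.2% | 7.1 | 68.4% | 60.8% |
| 50 | 36.0% | 8.2 | 59.8% | 52.8% |

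With n = 45 (stated 6.1), the error rate and detectable difference are 28.6% and 7.3 for m = 100, 24.6% and 6.7 for m = 200, and 22.4% and 6.4 for m = 400.

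**Step 4: check by simulation.** With 100,000 replicates at n = 49, the planned test rejected a true null in 35.8%, 29.3%, 24.7% and 22.6% of runs for m = 50, 100, 200 and 400.

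**The case against.** The strongest reply is that 5.9 is not an arithmetic error. For the null hypothesis that the study mean equals the published value, 20% is exact and 5.9 and 6.1 are right, and testing a single arm against a fixed benchmark is a familiar phase II design. That would answer the point if the plan stated such a null. It does not: sections 2.1 and 13.1 both describe a comparison with treated patients.

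Second, the size rests on an assumed m, and at m = 400 the effect is modest. The 19.2 is also not tied to a particular arm. Both are true, so no single corrected figure can be given. But the plan omits m, so its reader cannot tell which row of the table applies.

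Third, sections 13.1 and 13.3 call the study descriptive and admit that power may be short. No decision rule hangs on the test, and the sample size was not derived from the 5.9. This limits the damage, but the admission is not linked to uncertainty in the comparator and does not correct the stated level or detectable difference.

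Fourth, 13.1 specifies no confidence interval, so a misleading interval is a risk at reporting and not something the plan prescribes. That is fair.

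Finally, a two-sample test does not remove bias from a non-concurrent, differently treated comparator. That is correct; it is a separate problem, and none of the figures above includes it.

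**Conclusion.** The concern holds. The stated objective compares two groups, the specified test gives one of them zero variance, and the plan's own detectable differences confirm that nothing was allowed for it. The true error rate is above 20% for any finite IV arm, and the corrected detectable difference rounds above 5.9 unless that arm had more than about 1,100 patients with a 6-week score. For m between 100 and 400 the error rate is 29% to 23%, the detectable difference 7.1 to 6.2, and power at 5.9 is 68% to 77%. These sizes assume a common SD of 19.2, 49 patients analysed, and historical patients comparable with those enrolled. The direction is certain; the size stays open until m is supplied.

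**What to change.** In section 13.1, replace the one-sample test with a two-sample Welch t-test computed from summary data: mean, SD and number of patients for the study sample, and the same three quantities for the published IV arm at 6 weeks. Report the difference with its 80% confidence interval, which matches the test level, and its 95% interval.

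In section 13.3, state the IV-arm sample size and SD, say which arm the 19.2 describes, and restate the detectable difference from 19.2 × √(1/n + 1/m). It will be about 6.2 to 7.1 if m lies between 100 and 400. If the cited report gives a standard error instead of an SD, that can be entered directly. If it gives neither, show the result over a stated range of m.

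If the sponsor does mean to test against a fixed benchmark, sections 2.1 and 13.1 should say so, and the conclusions should be worded as conditional on that value. This is the weaker choice, because it no longer answers the objective as written.

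The cost is two sentences in 13.1 and a slightly less favourable figure in 13.3. No extra patients or data collection are needed, since 13.1 already relies on the published summary data. The one thing to confirm is that the IV-arm number and its SD or standard error at 6 weeks can be obtained from the cited report.

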13.2 Analysis of Secondary Objective

13.2.1 To describe QOL in patients with advanced ovarian cancer treated with SOC NAC followed by CRS with HIPEC as determined by the FACT-O questionnaire at 3 and 6 months post-treatment, the distribution of QOL at 3 and 6 months post-treatment will be examined. The descriptive statistics of QOL at 3 and 6 months post-treatment will be presented. In addition, the longitudinal data of QOL over time will be displayed graphically with individual trajectories.

13.2.2. To describe neurotoxicity at the end of study, the descriptive statistics will be presented. Since neurotoxicity is a 4-item measure from FACT/GOG-NTX4, counts and percentages will be calculated. Mean and standard deviation will be also calculated.

A Phase II Trial Evaluating Quality of Life After HIPEC in Patients with Stage IIIC and IV Ovarian, Fallopian Tube or Primary Peritoneal Carcinoma
Wake Forest Baptist Comprehensive Cancer Center (WFBCCC)
CCCWFU 83216

13.2.3. To describe abdominal discomfort at the end of study, the descriptive statistics will be presented. The abdominal discomfort is a 4-item score from FACT-GOG/AD. Counts and percentages will be calculated. Mean and standard deviation will be also calculated.

13.2.4. The toxicities will be measured by the number and severity of adverse events defined by CTCAE v5.0. Counts and percentages will be calculated for each adverse event. Mean, standard deviation, median, and interquartile range will be calculated for number of adverse events.

13.2.5. The response rate using RECIST criteria at each time point will be estimated. Counts and percentages will be calculated.

13.2.6. This secondary objective is to estimate progression free survival using survival analysis. Survival will be measured up to the time until progression, date of last contact, or death, whichever comes first. Kaplan-Meier survival curves will be used to estimate the survival probabilities. The survival probabilities for the whole sample and for the stratified groups (weekly or 3-weekly) will be calculated. The log-rank test will be used to compare the two stratified groups.

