5.2 Secondary Outcomes

- 5.2.1 QOL in patients with advanced ovarian cancer treated with SOC NAC followed by CRS with HIPEC as determined by the FACT-O questionnaire at 3 and 6 months post-treatment
- 5.2.2 Neurotoxicity in patients with advanced ovarian cancer treated with SOC NAC followed by CRS with HIPEC as determined by the FACT/GOG-NTX questionnaire
- 5.2.3 Abdominal discomfort in patients with advanced ovarian cancer treated with SOC NAC followed by CRS with HIPEC as determined by the FACT/GOG-AD questionnaire
- 5.2.4 Toxicities in patients with advanced ovarian cancer treated with SOC NAC followed by CRS with HIPEC (for one year post-op) as indicated by the number and severity of adverse events as defined by CTCAE v5.0
- 5.2.5 Response rates using RECIST v1.1 criteria in patients with advanced ovarian cancer treated with SOC NAC followed by CRS with HIPEC – at 3, 6, and 12 months post surgery.
- 5.2.6 PFS in patients with advanced ovarian cancer treated with SOC NAC followed by CRS with HIPEC

A Phase II Trial Evaluating Quality of Life After HIPEC in Patients with Stage IIIC and IV Ovarian, Fallopian Tube or Primary Peritoneal Carcinoma
 Wake Forest Baptist Comprehensive Cancer Center (WFBCCC)
 CCCWFU 83216

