6.0 Treatment Plan

6.1 Study-Related Interventions

	Pre-Study ^a	O.R. Day (surgery)	Follow-up Post-Treatment Visits (+/- 2 weeks)			
			6 weeks	3 Mo	6 Mo	12 Mo
Informed consent	X					
Demographics	X					
Medical history	X		X	X	X	X
Concurrent meds	X	X	X	X	X	X
Height, Weight, BSA	X		X	X	X	X
Op Note, Path Report, Perfusion Flowsheet		X				
Adverse event evaluation		X ^d	X ^d			
Physical exam and ECOG PS	X		X	X	X	X
Vital signs	X	X	X	X	X	X
B-HCG ^c	X					
CBC w/diff, plts	X			X	X	X
CMP	X			X	X	X
CA-125	X			X	X	X
CT of Abdomen, pelvis ^b	X			X	X	X
FACT-O, FACT/GOG-NTX, and FACT/GOG-AD questionnaires	X		X	X	X	

a: Pre-Study visit will occur and pre-study procedures will be completed within 28 days prior to registration.

b: CT of abdomen/pelvis as per standard-of-care.

c: B-HCG is for women of child-bearing potential only.

d: Adverse event monitoring will begin at time of surgery and will continue for six (6) consecutive weeks. AEs will be recorded in WISER at the 6 week time point.

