8.3 Methods for Evaluation of Quality of Life

The principal parameters employed to assess the QOL and symptoms are the following self-administered questionnaires: FACT-O (FACT-G with 27 items plus 12 items specific to ovarian cancer). These questionnaires are to be completed at eight time points. The primary outcome will address FACT-O scores, but additional assessments of abdominal pain by FACT/GOG-AD and neurological symptoms by FACT/GOG-Ntx.

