8.2 Quality of Life

Patient reported outcomes will be assessed at four time points:

- 1) Once at the pre-study visit.
- 2) At week 6 post-surgery
- 3) At months 3 and 6 in follow-up (post-op)

A Phase II Trial Evaluating Quality of Life After HIPEC in Patients with Stage IIIC and IV Ovarian, Fallopian Tube or Primary Peritoneal Carcinoma
Wake Forest Baptist Comprehensive Cancer Center (WFBCCC)
CCCWFU 83216

Patients' QOL, neurological symptoms and abdominal discomfort will be assessed with patient self-administered questionnaires.

QOL will be measured using the Functional Assessment of Cancer Therapy-Ovarian (FACT-O) questionnaire. The FACT-O is a multidimensional QOL questionnaire developed and validated for use by ovarian cancer patients; it includes 4 subscales: Physical Well-Being (7 items), Social Well-being (7 items), Functional Well-Being (7 items), Emotional Well-Being (6 items) and Additional Ovarian Cancer Concerns (12-items). These subscales can be analyzed separately or aggregated to produce a total score. The FACT-O has demonstrated reliability, validity, and responsiveness to change over time 31 as well as sensitivity to improvements in QOL experienced by patients responding to platinum/taxane therapy. The 4-item FACT/GOG-NTX4 (neurotoxicity) subscale will be used to assess patient reported symptoms of neurotoxicity. The FACT-GOG/Abdominal Discomfort (AD) measure will be used to assess abdominal discomfort. The FACT/GOG-AD is a four item measure (two included in the FACT-O) which measures abdominal symptoms, with average inter-item correlations of 0.64, an internal consistency of 0.875, and responsiveness to change over time computed on study data prior to the 4th cycle of chemotherapy by Huang, et al 2007.¹⁵

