Appendix J – FACT/GOG - NTX

Study Number: 83216 PID: _____

Investigator: [name]. Date: ____ / ____ / ____

Below is a list of statements that other people with your illness have said are important. **Please circle or mark one number per line to indicate your response as it applies to the past 7 days.**

NTX 1
NTX 2
NTX 3
NTX 4

		Not at all	A little bit	Som e-what	Quite a bit	Very much
NTX 1	I have numbness or tingling in my hands	0	1	2	3	4
NTX 2	I have numbness or tingling in my feet	0	1	2	3	4
NTX 3	I feel discomfort in my hands	0	1	2	3	4
NTX 4	I feel discomfort in my feet	0	1	2	3	4

Please circle or mark one number per line to indicate your response as it applies to the past 7 days.

NTX 5
HI1 2
NTX 6
NTX 7
NTX 8

	ADDITIONAL CONCERNs	Not at all	A little bit	Som e-what	Quite a bit	Very much
NTX 5	I have joint pain or muscle cramps	0	1	2	3	4
HI1 2	I feel weak all over	0	1	2	3	4
NTX 6	I have trouble hearing	0	1	2	3	4
NTX 7	I get a ringing or buzzing in my ears	0	1	2	3	4
NTX 8	I have trouble buttoning buttons	0	1	2	3	4

NTX
9

I have trouble feeling the shape of small objects
when they are in my hand

0 1 2 3 4

An6

I have trouble walking

0 1 2 3 4

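### Neurotoxicity is analysed as a 4-item score at study end, although the form holds 11 items and is collected four times; no analysis is stated for the other seven items

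*Combined protocol and SAP*

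**What the plan says.** Two descriptions of the neurotoxicity measure run through the combined protocol and SAP.

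**The 4-item NTX4.** Section 8.2 (Quality of Life) states: "The 4-item FACT/GOG-NTX4 (neurotoxicity) subscale will be used to assess patient reported symptoms of neurotoxicity". Section 13.2.2 follows it with the words "Since neurotoxicity is a 4-item measure from FACT/GOG-NTX4", and plans counts, percentages, a mean and a standard deviation. The first form list in section 12.0 also uses this name: "FACT-O, FACT-GOG-NTX4, FACT/GOG-AD (Appendices H, I, J".

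**FACT/GOG-NTX, with no item limit.** Section 5.2.2 defines the secondary outcome "as determined by the FACT/GOG-NTX questionnaire". The visit schedule in 6.1 lists "FACT-O, FACT/GOG-NTX, and FACT/GOG-AD questionnaires". Section 8.3 refers to "neurological symptoms by FACT/GOG-Ntx". The submission schedule in 12.0 also says FACT/GOG-NTX.

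Section 12.0 says that the appendices hold the master case report forms. Appendix J, titled FACT/GOG - NTX, prints NTX1 to NTX4 and then a second block of items, one of which is "I have trouble hearing".

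On timing, 13.2.2 describes neurotoxicity at the end of the study and names no other visit.

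**The concern.** Objective 2.2.2 is to describe neurotoxicity after neoadjuvant chemotherapy, cytoreductive surgery and HIPEC. It is not limited to numbness and discomfort in the hands and feet, which is all that NTX1 to NTX4 ask about. An analyst who follows 13.2.2 literally would tabulate those four items and leave the rest of the completed form without a planned use. An analyst who starts from 5.2.2 and Appendix J could reasonably compute an 11-item total. The two results would lie on different scales.

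Timing adds to this. Section 3.1.3 requires three to six cycles of carboplatin-doublet chemotherapy before entry, so some patients may already have nerve symptoms at the pre-study visit. A single summary at study end cannot separate symptoms already present from those that appear or worsen after surgery. The pre-study form is collected and would allow this.

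**Working it through.** No sample-size or power formula applies. The check is a count of items and a comparison of sections.

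**Step 1. Items in Appendix J.**

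| Group | Items | Count |
|---|---|---|
| Numbness or discomfort, hands and feet | NTX1, NTX2, NTX3, NTX4 | 4 |
| Hearing and tinnitus | NTX6, NTX7 | 2 |
| Hand function | NTX8, NTX9 | 2 |
| Joint or muscle pain, weakness, walking | NTX5, HI12, An6 | 3 |

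Total: 4 + 2 + 2 + 3 = 11. The plan's figure of 4 in 13.2.2 matches the first group only.

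**Step 2. Share without a stated analysis.** 11 − 4 = 7 items, and 7/11 = 64%. No section says how these seven are scored, analysed or reported.

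**Step 3. Scale.** Each item is answered 0 to 4. The raw range is 4 × 4 = 16 points for NTX4 and 11 × 4 = 44 points for the whole form. The mean and standard deviation promised in 13.2.2 therefore depend on which measure is meant.

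**Step 4. Visits.** Section 8.2, the 6.1 schedule and the 12.0 submission schedule agree on four time points: pre-study, 6 weeks, 3 months and 6 months. (Section 8.3 says eight, which none of those three supports.) The 12-month visit has no questionnaires in 6.1, and Appendix F says the same. The last form available for a study-end summary is therefore the 6-month one, and 13.2.2 gives the three earlier forms no stated role.

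**Step 5. Amount of data.** Assuming the 50 patients in 13.3 all complete every form, the seven items yield up to 7 × 4 × 50 = 1,400 answers with no planned use. This is an upper bound, since dropout and missing forms reduce it.

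**Step 6. Comparison within the plan.** For abdominal discomfort, 13.2.3 plans a 4-item score and Appendix I prints four items. The mismatch between form and planned score is specific to neurotoxicity.

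**Step 7. Do the adverse event tables cover the gap?** Section 13.2.4 tabulates CTCAE events, which could include hearing or motor events. Note d of the 6.1 schedule and section 9.2 end monitoring six weeks after surgery; 6.5 says 30 days. Only 5.2.4 says one year, and 6.1 has no adverse event evaluation after week 6. Cover is therefore clinician-graded and, under the visit schedule, stops at about six weeks. At 3 and 6 months, the seven items are the only structured record of these symptoms that the schedule provides.

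**The case against.** The strongest reply is that NTX4 is a specified choice. The measurement section (8.2) and the analysis section (13.2.2) agree on it, and 12.0 uses the name once. The sections that say FACT/GOG-NTX give no item count or scoring rule, so one can read the form as what is administered and NTX4 as what is scored. Appendix J prints NTX1 to NTX4 as a separate first block. Reference 15, cited in 8.2, has a title that speaks of reducing the Ntx subscale; only the title is visible here, so it settles nothing, but it fits a deliberate short score. This objection stands to the extent that nothing in the documents shows the 11-item total to be the better outcome.

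It does not remove the gap. If NTX4 is intended, 5.2.2 should say so, and the plan should state what the other seven items are for.

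A reader might infer that hearing and motor symptoms will never be reported. The documents do not support that: 13.2.2 is silent on the other items and does not exclude them, and the CTCAE tables give partial cover. A reader might also point to the carboplatin table in section 9.1, which lists ototoxicity (12%) separately from peripheral neuropathies (13%). Those figures come from a trial of carboplatin against cisplatin, not from a single HIPEC perfusion. They show that hearing effects are a distinct category, but they predict no rate for this trial.

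**Conclusion.** The inconsistency is real and minor. Seven of 11 collected items (64%), including both hearing items, have no stated analysis. The outcome's name and raw range (0–16 or 0–44) differ according to the section read, although 8.2 and 13.2.2 together favour NTX4. Section 13.2.2 uses one time point where four are collected.

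The 64% is a share of items, not a bias in any estimate. This is a descriptive secondary outcome, and the power calculation in 13.3 concerns only the FACT-O primary objective. The conclusion assumes that Appendix J as printed is the form patients complete, as 12.0 indicates. It does not require that NTX4 be the wrong choice.

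**What to change.** 1. Name one neurotoxicity score as the outcome, with its item list and range, and use the same name in 5.2.2, 8.2, 12.0 and 13.2.2. NTX4 may stay as that score.
2. In 13.2.2, also describe the remaining seven Appendix J items, with the two hearing items shown, or give the 11-item total as a labelled supplementary score.
3. Replace the single study-end summary with summaries at pre-study, 6 weeks, 3 months and 6 months, and change from pre-study at each later visit.

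The cost is wording in four sections and one more descriptive table. No new data, visits or patients are needed, and the primary analysis and sample size do not change.
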